6 STUDY AGENT

6.1 Study Agent(s) and Control Description

This study does not involve an investigational drug and is therefore, CTA exempt.

7 STUDY SPECIFIC PROCEDURES

7.1 Study Procedures/Evaluations

The study-specific procedures and time-points to be done over the course of the study are summarized below and in Section 7.3 of the protocol:

Enrolled Study Population (both study groups)

- Informed Consent (enrolment, visit 0)
- Final study eligibility assessment including administration of DSI (enrolment, visit 0)
- Randomization (baseline)
- Collect Baseline Demographics age; gender; ethnicity/race (baseline, visit 1)
- Collect Past Medical History cause of end stage renal disease; diabetes; hypertension; smoking; cardiac disease/arrythmia; cerebrovascular disease/stroke/transient ischemic attack; lung disease; peripheral vascular disease/lower extremity amputation; arthritis; date of dialysis start; other relevant medical history (baseline, visit 1)
- Collect Concomitant Medications (each study visit)
- Collect vital signs/clinical data height, weight, BMI, systolic and diastolic blood pressure; dialysis adequacy (Kt/V); weekly intradialytic fluid gains; duration of HD and heart rate (each study visit; height will only be done on the 1st baseline visit)
- Collect Clinical Laboratory results (each study visit):
 - o Blood: hemoglobin, calcium, albumin, phosphate
- Patient compliance with the study protocol will be monitored in accordance to the Monitoring Plan (each study visit)
- Dialysis Symptom Index (enrolment visit and each study visit)
- EQ-5D-5L (each study visit)
- Time required for recovery following hemodialysis (each study visit)
- Download 7 day accelerometry history (each study visit)
- Godin-Shephard Leisure-Time Exercise Questionnaire (each study visit)
- Incremental Shuttle Walk Test (each study visit)
- Frailty status using the Modified Fried Criteria (each study visit)
- Self-Efficacy for Exercise Survey (each study visit)
- Cause and length of any hospitalization since last study visit (study visit 2, 3 and 4)
- Death (study visit 2, 3 and 4)

 Physical activity/exercise logs (collected weekly for first 12 weeks then every 2 weeks for next 40 weeks)

Intervention Group – Additional Evaluation

 Maximal incremental cycle test to volitional exhaustion⁷⁸ (After randomized to intervention and before intervention started)

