4 STUDY DESIGN AND ENDPOINTS

4.1 Description of the Study Design

This is a Phase 4 single-center prospective randomized controlled trial of prevalent adult chronic HD patients. Patients will be screened for eligibility **and one hundred and fifty patients** with dialysis-related symptoms as confirmed by baseline DSI symptom burden score > 0 will undergo 1:1 randomization to the two-step intervention (intensive and maintenance phase) and control arms for 1 year. The total study duration is approximately 4 years.

Please see the Schematic of the Study Design, p. 8.

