5.2 Participant Enrolment Exclusion Criteria

Individuals meeting any of the following criteria will be excluded from participation:

- 1. Acute coronary syndrome in the past 3 months;
- 2. Unstable arrhythmia;
- 3. Shortness of breath at rest or with minimal activity (NYHA Class 4);
- 4. Symptomatic hypoglycemia (>2x/week in week prior to enrolment);
- 5. Currently participating in the Manitoba Renal Program's clinical intradialytic cycling program;
- 6. Score of '0' on Dialysis Symptom Index when administered at time of consent;

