7.2 Study Outcome Evaluations

Outcome assessments (as detailed in Section 4.2) will occur at baseline, 12, 26 and 52 weeks (within +/-10 days of this time point) and be performed pre-dialysis on a midweek dialysis day to minimize the effects of fluid overload and dialysis fatigue, but maximize convenience and adherence to the assessment schedule. In our pilot study, assessment visits took 30 minutes.

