7.3 Study Schedule

A detailed description of each study procedure is available in Section 7.1:

Scheduled Study Procedure	Screening/ Enrolment (Visit 0)	Baseline (Visit 1)	End Intervention 12 weeks (Visit 2)	Wash-Out Visit 26 weeks (Visit 3)	Final Visit 52 weeks (Visit 4)
Informed Consent	Х				
Final Study Eligibility	Х	Χ			
Demographics		Х			
Medical History		Х			
Physical/Clinical Assessment		Х	Х	Х	Х
Concomitant Medications		Х	Х	Х	Х
Safety Monitoring Adverse Events		Х	Х	Х	х
Protocol Compliance		Х	Х	Х	Х
Dialysis Symptom Index	Х	Х	Х	Х	Х
EQ5D-5L/EQVAS		Х	Х	Х	Х
Time to recover from HD		Х	Х	Х	Х
Accelerometry		Χ	Х	Х	Х
Godin-Shephard Leisure Time Exercise Questionnaire		Х	Х	Х	х
Incremental Shuttle Walk Test		Х	Х	Х	х
Frailty Status		Х	Х	Х	Х
Self-Efficacy for Exercise Study		Х	Х	Х	х
Hospitalization history			Х	Х	Х
Death			Х	Х	Х
Collection of exercise logs			WEEKLY	EVERY 2 W	/EEKS
Incremental Cycle Test	(X)*				
*In intervention group only be	tween enrolm	ent visit an	d start of interventio	n	

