9.3 Description of Statistical Methods

9.3.1 Primary Outcome

Developed in consultation with a statistician ([name], Chronic Disease Innovation

Centre) familiar with RCTs and our study outcomes, analysis will be performed in an intention-to-treat manner on a case available basis. Change in DSI severity score from baseline to 12 weeks will be compared between groups by independent two-tailed t-test or Mann-Whitney U test depending on distribution and using generalized linear mixed models with study timepoint as a random effect and adjusted for baseline DSI score. In a subgroup of individuals whose baseline DSI score is >7, the proportion of individuals whose DSI severity score has improved by 7 or more points from baseline to 12 weeks will be compared between groups at each study time point using Chi-square test.

Multiple logistic regression will be performed to determine predictors of a >7 point change in DSI severity score over time and adjusted for time varying confounders using a marginal structural model. Interaction terms for sex and baseline DSI score will also be inputted into the model. Although study group will be the primary predictor in this model, other key predictors of symptom burden (including baseline DSI score, diabetes status, ischemic heart disease (IHD), age, gender, race, smoking status, serum albumin level, hemoglobin, baseline physical function, physical activity level and interaction terms for gender/intervention and baseline DSI score/intervention) will also be tested in a step-wise manner.

If **missing outcome data** is greater than anticipated (25%) we will impute them according to current FDA/NAS/NRC recommendations using multiple imputation with chained equations ⁸⁶⁻⁸⁸. Specifically, multiple imputation creates 20-40 complete datasets with plausible values from the model-based predictive distributions, and pooled estimates and standard errors are obtained through the use of Rubin's combining rules. These models are predicated on the assumption that the data are missing at random (MAR). Finally, the robustness of the inferences about treatment effects to violations of the MAR assumptions will be evaluated through a sensitivity analysis ⁸⁸.

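### The DSI is scored twice before randomisation, but the adjusted models use one baseline score; adding the consent-visit score as a second covariate is a small, nearly free gain in precision

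*Combined protocol and SAP*

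**What the plan says.** Section 7.1 lists the "Dialysis Symptom Index (enrolment visit and each study visit", and the schedule in 7.3 marks the DSI at both Visit 0 and Visit 1. The Visit 0 score has one stated job: 7.1 describes a "Final study eligibility assessment including administration of DSI (enrolment, visit 0"), and 5.2 excludes a "Score of '0' on Dialysis Symptom Index when administered at time of consent". Under 7.3.2 the randomisation code is withheld until baseline testing is done, so both scores precede allocation.

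The schedule heads its second column "Baseline (Visit 1"). Section 7.3.1 arranges the baseline assessment after eligibility is confirmed and places the baseline outcome testing there. Section 7.2 requires outcome assessments to "be performed pre-dialysis on a midweek dialysis day"; no timing relative to dialysis is given for the Visit 0 DSI. Section 4.1 is the exception on labelling: it describes participants as having symptoms "confirmed by baseline DSI symptom burden score > 0", although that eligibility check belongs to consent.

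In 9.3.1 the mixed models for the DSI are "adjusted for baseline DSI score", with no visit number. Section 9.3.3 repeats the primary analyses at 26 and 52 weeks.

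**The concern.** A symptom score with one-week recall varies from week to week within a patient. One pre-randomisation score is therefore a noisy measure of the patient's usual symptom level, and a second score, taken in both arms before allocation, carries some further information about it. The plan collects that second score and gives it no analysis role. At stake is some precision in the baseline-adjusted comparisons of DSI between arms, which could be had without a new visit or new data.

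**Working it through.** **The plan's own figure.** Section 9.2 gives 58 per arm for 50% versus 25% responders, 80% power, alpha 0.05. With the pooled-variance formula, two-sided:

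n = [1.96 × √(2 × 0.375 × 0.625) + 0.842 × √(0.50 × 0.50 + 0.25 × 0.75)]² / 0.25² = 57.7, so 58.

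This reproduces. It is a comparison of two proportions with no covariates, so the point raised here leaves it unchanged.

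**Inputs for the covariate gain.**
- SD of the DSI score: 30 (4.2.1, pilot, n = 18).
- SD of the change in DSI: 16 (9.2).
- Correlation between Visits 0 and 1, r01: not in the documents. Assumed 0.90-0.95, with equal correlation across all visits as the upper case.
- Correlation between Visit 0 and week 12, r0: not in the documents. Assumed 0.83-0.86, at or slightly below the Visit 1 value.

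**Implied correlation of Visit 1 with week 12**, assuming equal variances at the two visits:

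r1 = 1 − 16² / (2 × 30²) = 1 − 256/1800 = 0.858.

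**Residual variance as a share of the score variance.**
- Visit 1 only: 1 − r1² = 0.264.
- Visits 0 and 1: 1 − (r1² + r0² − 2 × r1 × r0 × r01) / (1 − r01²).

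| r01 | r0 | Residual share, both scores | Ratio to 0.264 | Reduction |
|---|---|---|---|---|
| 0.858 (all equal) | 0.858 | 0.208 | 0.79 | 21% |
| 0.90 | 0.86 | 0.223 | 0.85 | 15% |
| 0.90 | 0.83 | 0.247 | 0.93 | 7% |
| 0.95 | 0.86 | 0.243 | 0.92 | 8% |
| 0.95 | 0.83 | 0.262 | 0.99 | 1% |

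The standard error scales with the square root of the ratio. A 15% reduction in variance shortens it by about 8% (√0.85 = 0.92), a 1% reduction by about 0.5% (√0.99 = 0.995), and the 21% upper case by about 11% (√0.79 = 0.89).

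**Sensitivity to the 0.858.** A pilot SD from 18 patients is imprecise: its normal-theory 95% interval is about 22.5 to 45, which moves r1 from 0.75 to 0.94. With r0 = r1 the residual share is 1 − 2r1²/(1 + r01). At r01 = 0.95 the reduction is then about 3% for r1 = 0.75 (0.423/0.4375 = 0.97) and about 19% for r1 = 0.94 (0.0937/0.1164 = 0.81). The gain is small to moderate, and its exact size is unknown.

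The documents give no SD of change at 26 or 52 weeks, so the gain is not sized there.

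**The case against.** The strongest reply is that adjusting for one designated baseline is standard practice and not an error, that the Visit 0 score already does its stated job, and that adjacent visits probably correlate highly, which puts the gain towards the low end. All of that stands. So does the point that the powered responder comparison is a Chi-square test, which takes no covariates and gains nothing.

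A reader might infer something stronger: that baseline is undefined, so the 7-point responder call depends on an unstated choice of visit. Under assumed Visit 0/Visit 1 correlations of 0.858 to 0.97, switching visits would indeed reclassify about 12-33% of patients. The documents do not support that reading as a defect. Sections 7.2, 7.3 and 7.3.1 together place the outcome baseline at Visit 1, and the contrary label rests on one sentence in 4.1. Even that sentence is not a clear conflict, because the schedule marks final eligibility at both visits.

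A reader might also infer that the Visit 0 score is thrown away or that the comparison is biased. The plan says neither that the score is discarded nor that it will be used; it only gives it no analysis role. Both scores precede allocation, so either choice treats the arms alike.

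**Conclusion.** The point holds as a minor improvement in efficiency. Two pre-randomisation DSI scores exist, and the adjusted models use one. Adding the other would cut residual variance in the adjusted 12-week model by about 1-15% for an assumed Visit 0/Visit 1 correlation of 0.90-0.95, and by 21% if all visits are equally correlated. These figures rest on the implied correlation of 0.858, equal variances across visits and assumed visit-to-visit correlations. The unstated timing of Visit 0 relative to dialysis may lower its correlation with later scores, but does not make it invalid as a covariate. Naming the baseline visit is a wording clarification that changes no number.

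**What to change.** In 9.3.1 and 9.3.3, pre-specify that the baseline-adjusted DSI models at 12, 26 and 52 weeks include the Visit 0 DSI as a second pre-randomisation covariate alongside the Visit 1 DSI. As accompanying wording, state in 4.2.1 and 9.3.1 that Visit 1 is the baseline for the change score, the responder definition and the subgroup with baseline DSI above 7, and in 4.1 call the eligibility score the consent-visit (screening) DSI.

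The cost is one degree of freedom per model and a few words. No new data, visit or change to the sample size is needed. The covariate should be fixed before unblinded data are seen, so that its inclusion is not a choice made at analysis.

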7.1.1 Demographic Data Collection

The research assistant will collect demographic data at the baseline assessment visit via patient interview and hemodialysis chart review. Data collected will include age, gender, race, cause of renal failure, dialysis vintage (time on hemodialysis), comorbidities (cardiovascular disease, congestive heart failure, diabetes mellitus, arthritis, peripheral vascular disease, cerebrovascular disease, malignancy, lung disease), use of walking aid (type), smoking history.

7.1.2 Clinical Data Collection

The research assistant will collect clinical data at baseline, 12, 26, and 52-week assessment visits via hemodialysis chart review. Data collected will include the following:

- 1. **Medications:** (eprex weekly dose, blood pressure medications and dosage, cardiac medications). The research assistant will photocopy the most recent de-identified Renal Medication Flow sheet in the hemodialysis chart to include in the research chart.
- 2. **Dialysis Clearance**: mean Kt/V for the 3 HD sessions immediately preceding the study assessment
- 3. **Blood pressure:** Systolic and diastolic blood pressure pre and post hemodialysis at the hemodialysis session immediately preceding the study assessment
- 4. **Heart Rate:** Heart rate (sitting) pre and post hemodialysis at the hemodialysis session immediately preceding the study assessment
- 5. **Duration and frequency** of hemodialysis sessions
- 6. **Dialysis prescription:** Dialysis time, frequency of HD sessions, Dialysate potassium, sodium and calcium, dry weight
- 7. **Mean fluid gains:** the total volume (L) of fluid gained between interdialytic sessions during the week (3 HD sessions) prior to the study assessment

7.1.3 Laboratory Data Collection

The research assistant will collect laboratory data 12, 26, and 52-week assessment visits via hemodialysis chart review. The monthly blood work results taken at the closest time point to the study visit will be transcribed to CRF forms from HD chart at each study assessment time point. Monthly blood work samples are taken pre-dialysis on a mid week dialysis day routinely as standard of care in in-centre hemodialysis. Hardcopy print out of results is placed in the hemodialysis chart as routine standard of care. Lab results collected

will include: Hemoglobin, albumin, potassium, calcium, phosphate, parathyroid hormone. No additional blood samples will be required for this study.

7.2 Study Outcome Evaluations

Outcome assessments (as detailed in Section 4.2) will occur at baseline, 12, 26 and 52 weeks (within +/-10 days of this time point) and be performed pre-dialysis on a midweek dialysis day to minimize the effects of fluid overload and dialysis fatigue, but maximize convenience and adherence to the assessment schedule. In our pilot study, assessment visits took 30 minutes.

7.3 Study Schedule

A detailed description of each study procedure is available in Section 7.1:

Scheduled Study Procedure	Screening/ Enrolment (Visit 0)	Baseline (Visit 1)	End Intervention 12 weeks (Visit 2)	Wash-Out Visit 26 weeks (Visit 3)	Final Visit 52 weeks (Visit 4)
Informed Consent	Х				
Final Study Eligibility	Х	Χ			
Demographics		Х			
Medical History		Х			
Physical/Clinical Assessment		Х	Х	Х	Х
Concomitant Medications		Х	Х	Х	Х
Safety Monitoring Adverse Events		Х	Х	Х	х
Protocol Compliance		Х	Х	Х	Х
Dialysis Symptom Index	Х	Х	Х	Х	Х
EQ5D-5L/EQVAS		Х	Х	Х	Х
Time to recover from HD		Х	Х	Х	Х
Accelerometry		Χ	Х	Х	Х
Godin-Shephard Leisure Time Exercise Questionnaire		Х	Х	Х	х
Incremental Shuttle Walk Test		Х	Х	Х	х
Frailty Status		Х	Х	Х	Х
Self-Efficacy for Exercise Study		Х	Х	Х	х
Hospitalization history			Х	Х	Х
Death			Х	Х	Х
Collection of exercise logs			WEEKLY	EVERY 2 W	/EEKS
Incremental Cycle Test	(X)*				
*In intervention group only be	tween enrolm	ent visit an	d start of interventio	n	

7.3.2 Randomization and Blinding

Participants will be randomly assigned to the Intervention Arm or Control Arm. Randomization will be performed by a third party using *block randomization* with randomly permuted block sizes with an overall 1:1 allocation. To ensure *allocation concealment* and *to minimize bias*, the randomization code will not be released until baseline testing is completed. After randomization has occurred, the site's research staff will be responsible for ensuring the assigned randomization number is applied to all study documents for each participant. Due to the nature of the intervention in this trial, randomization to the Intervention Arm cannot be blinded to the site PI's or participants. However outcome assessors and study statistician will be blinded to study group during analysis (Prospective Randomized Open Blinded-Endpoint study).

7.4 Study Groups

7.4.1 Control Arm, Standard-of-care

As recommended in clinical practice guidelines for individuals with CKD, participants will receive standardized exercise counseling at baseline.^{76, 77} Although not prohibited from participating in exercise outside of the study protocol, participants in the control group will not undergo a formal structured exercise intervention and will be asked to refrain from intradialytic cycling during the 12-week intervention period. Exercise activity will be tracked via weekly self-reported log sheets. The study kinesiologist (to control for personal trainer effect) will collect log sheets weekly during the study period. Outcome measurements will occur according to the Schedule of Events (Section 7.5).

7.4.2 Intervention Arm, Exercise Rehabilitation Program

Participants will receive exercise counseling as per controls. To standardize intervention exercise intensity, a maximal incremental cycle test (to volitional exhaustion)⁷⁸ will be performed prior to hemodialysis on a mid-week dialysis day on an ergometer in the hemodialysis unit or at the Wellness Institute depending on availability of testing equipment and patient preference. Participants will then participate in a 12-week exercise rehabilitation program as follows (See Section 7.4.5 Study Intervention Schematic):

- 1. Standardized one-on-one lifestyle education sessions at HD provided by the study kinesiologist: Self-management exercise education using Wellness Institute Cardiac Rehabilitation program modules for 1 hr/wk during the first 4 weeks of the intervention. An additional 4 standardized sessions focused on maintenance of lifelong physical activity will be provided over the remaining intervention period.
- 2. Resistance training, using tubing and body weight, based on established guidelines:^{79, 80} Weekly resistance training education will be provided by the study kinesiologist in one-on-one format at HD during the first 4 weeks of intervention. Resistance training bands, instructions and logbooks provided for home exercise (goal 2 sessions/week) during the 26-week intervention period (See Section 7.4.6 Summary Exercise Rehabilitation Program).
- 3. Intradialytic cycling during HD (intensive and maintenance phase): Participants will cycle on TherapyCycleTM (Greely, CO) ergometers modified for dialysis beds or chairs⁸¹ with an initial target exercise intensity of 50-60% of individual maximal workload as determined by the incremental cycling test.^{49,82} Target exercise duration will be 60 minutes in the first half of each HD session, 3 times per week for 12 weeks. Rest periods will be provided as needed if participants are unable to complete 60 minutes of continuous exercise.^{82,83} Duration of total exercise time, average workload (Watts) and self-reported exercise intensity as measured by Borg Rating of Perceived Exertion (RPE) will be recorded by participants for each exercise session. Target Borg RPE will be 13, which is considered to be moderate intensity.⁸⁴ Ergometer resistance will be adjusted over time by the study kinesiologist as triggered by a 1-point change in Borg RPE.

During the initial 3 intradialytic exercise sessions, the study kinesiologist will supervise participants closely. Following 3 sessions (or more if required), HD unit staff will assist with set up of the cycle ergometers and monitoring during exercise sessions.

During the *intensive phase* of the intervention, the study kinesiologist will check in on a weekly basis (at a minimum) with participants and staff to address problems and questions as needed. Subsequently, during the *maintenance phase* of the intervention, the kinesiologist will check in every two weeks to help with intensity adjustment, encouragement, motivation and troubleshooting. All exercise activity performed outside of HD, including resistance training will be tracked weekly by self-report using home log sheets during the intervention phase and then bimonthly until study end (see Section 7.4.5 Study Intervention Design Schematic).

7.4.3 Exercise following the intervention period

If offered as a clinical program in their HD unit, participants will be able to participate in intradialytic cycling *after the intervention phase*, regardless of study group.

[figure not shown]
7.4.4 Adherence to the exercise intervention

Adherence to will be assessed in the intervention group by:

- (a) Proportion of resistance and intradialytic cycling exercise sessions logged compared to total number of possible exercise sessions
- (b) Proportion of total minutes of intradialytic cycling achieved based on logbook records compared to goal intradialytic cycling minutes.

7.4.5 Study Intervention Design Schematic

Figure 1: Study Design Schematic

7.4.6 Summary of Exercise Rehabilitation Program

Type of	Frequen	Time	Duration	Intensity	Location
Intervention	су				
One-on-One	1x/wk	1 hour	8 weeks	Not applicable	HD Unit
Exercise Education					
Resistance Exercise	2x/wk	8 muscle groups^	12 weeks	8 repetition max	Home
		Goal: 12-15		Goal RPE*= 12-13	
		reps/muscle			
Cycling during HD	3x/wk	Goal: 60 minutes	12 weeks	50-60% max workload	HD Unit
				(Cycling test)	
				Goal RPE=13	

[^] biceps, triceps, chest muscles, hamstrings, quadriceps, hip extensors and hip abductors

